12.0 Appendix

[Appendix A](#)

OMERACT Criteria

Appendix B

Analysis of Binary Endpoints

Appendix C

Analysis of Continuous Endpoints using Mixed Effect Model Repeat Measurement (MMRM)

Appendix A. OMERACT Criteria

Rheumatology Common Toxicity Criteria v.2.0

Based on Woodworth TG, et al. Standardizing assessment of adverse effects in rheumatology clinical trials II. Status of OMERACT Drug Safety Working Group May 2006: OMERACT 8. Standardizing Assessment and Reporting of Adverse Effects in Rheumatology Clinical Trials: Enabling Description of Comparative Safety Profiles for Antirheumatic Therapies

(Note that for L9. CPK and L11. Creatinine, the criteria in this table is replaced by the NCI CTC grade, as the NCI CTC grade is used for analysis for these two parameters.)

	1 – Mild Asymptomatic, or transient Short duration (< 1 week) No change in life style No medication or OTC	2 – Moderate Symptomatic Duration (1 – 2 weeks) Alter lifestyle occasionally Meds relieve. (may be prescription), Study drug continued	3 – Severe Prolonged symptoms, reversible, major functional impairment Prescription meds/partial relief May be hospitalized < 24 hr Temporary study drug discontinuation, or/and dose reduced	4 – Includes Life Threatening At risk of death Substantial disability, especially if permanent. Multiple meds Hospitalised > 24 hr Study drug discontinued
A. Allergic/Immunologic				
A1. Allergic reaction/ hypersensitivity (includes drug fever)	Transient rash: drug fever < 38°C; transient, asymptomatic bronchospasm	Generalised urticaria responsive to meds; or drug fever > 38°C, or reversible bronchospasm	Symptomatic bronchospasm requiring meds; symptomatic urticaria persisting with meds, allergy related oedema/angioedema	Anaphylaxis, laryngeal/pharyngeal oedema, requiring resuscitation
A2. Autoimmune reaction	Serologic or other evidence of autoimmune reaction, but patient asymptomatic: all organ function normal and no treatment is required (e.g., vitiligo)	Evidence of autoimmune reaction involving a non-essential organ or functions, requiring treatment other than immunosuppressive drugs (e.g., hypothyroidism)	Reversible autoimmune reaction involving function of a major organ or toxicity requiring short term immunosuppressive treatment (e.g., transient colitis or anaemia)	Causes major organ dysfunction, or progressive, not reversible, or requires long-term administration of high dose immunosuppressive therapy
A3. Rhinitis (includes sneezing, nasal stuffiness, post-nasal discharge)	Transient, non-prescription meds relieve	Prescription med. required, slow	Corticosteroids or other prescription med. with persistent disabling symptoms such as impaired exercise tolerance	NA

A4. Serum sickness	Transient, non-prescription meds relieve	Symptomatic, slow response to meds (e.g., oral corticosteroids)	Prolonged; symptoms only partially relieved by meds; parenteral corticosteroids required	Major organ dysfunction, requires long-term high-dose immunosuppressive therapy
A5. Vasculitis	Localised, not requiring treatment; or rapid response to meds; cutaneous	Symptomatic, slow response to meds (e.g., oral corticosteroids)	Generalised, parenteral corticosteroids required or/and short duration hospitalisation	Prolonged; hospitalisation, ischemic changes, amputation
B. Cardiac				
B1. Arrhythmia	Transient, asymptomatic	Transient, but symptomatic or recurrent, responds to meds	Recurrent/persistent; maintenance prescription	Unstable, hospitalisation required, parenteral meds
B2. Cardiac function decreased	Asymptomatic decline in resting ejection fraction by > 10%, but < 20% of baseline value	Asymptomatic decline of resting ejection fraction \geq 20% of baseline value	CHF responsive to treatment	Severe or refractory CHF
B3. Edema	Asymptomatic (e.g., 1 + feet/calves), self-limited, no therapy required	Symptomatic (e.g., 2 + feet/calves), requires therapy	Symptoms limiting function (e.g., 3 + feet/calves, 2 + thighs), partial relief with treatment prolonged	Anasarca; no response to treatment
B4. Hypertension (new onset or worsening)	Asymptomatic, transient increase by > 20 mmHg (diastolic) or to > 150/100 if previously normal, no therapy required	Recurrent or persistent increase > 150/100 or by > 10 mmHg (diastolic), requiring and responding readily to treatment	Symptomatic increase > 150/100, > 20 mmHg, persistent, requiring multi-agency therapy, difficult to control	Hypertensive crisis
B5. Hypotension (without underlying diagnosis)	Transient, intermittent, asymptomatic, orthostatic decrease in blood pressure > 20 mmHg	Symptomatic, without interference with function, recurrent or persistent > 20 mmHg decrease, responds to treatment	Syncope or symptomatic, interferes with function, requiring therapy and sustained medical attention, dose adjustment or drug discontinuation	Shock
B6. Myocardial ischaemia	Transient chest pain/ECG changes; rapid relief with nitro	Recurring chest pain, transient ECG ST-T changes; treatment relieves	Angina with infarction, no or minimal functional compromise, reduce dose or discontinue study drug	Acute myocardial infarction, arrhythmia or/and CHF

B7. Pericarditis/ pericardial effusion	Rub heard, asymptomatic	Detectable effusion by echocardiogram, symptomatic NSAID required	Detectable on chest x-ray, dyspnoea; or pericardiocentesis; requires corticosteroids	Pulsus alternans with low cardiac output; requires surgery
B8. Phlebitis/thrombosis/ Embolism (excludes injection sites)	Asymptomatic, superficial, transient, local, or no treatment required	Symptomatic, recurrent, deep vein thrombosis, no anticoagulant therapy required	Deep vein thrombosis requiring anticoagulant therapy	Pulmonary embolism
C. General (constitutional)				
C1. Fatigue/malaise (asthenia)	Increase over baseline; most usual daily functions maintained, short term	Limits daily function intermittently over time	Interferes with basic ADL, persistent	Unable to care for self, bed or wheelchair bound > 50% of day debilitating, hospitalisation
C2. Fever (pyrexia) (note: fever due to drug allergy should be coded as allergy)	Transient, few symptoms 37.7 – 38.5°C	Symptomatic, recurrent 38.6 – 39.9°C. Relieved by meds	≥ 40°C, ≤ 24 h, persistent symptoms; partial response to meds	≥ 40°C, debilitating, > 24 h, hospitalisation; no relief with meds
C3. Headache	Transient or intermittent, no meds or relieved with OTC	Persistent, recurring, non-narcotic analgesics relieve	Prolonged with limited response to narcotic medicine	Intractable, debilitating, requires parenteral meds
C4. Insomnia	Difficulty sleeping, short term, no interfering with function	Difficulty sleeping interfering with function, use of prescription med	Prolonged symptoms, with limited response to narcotic meds	Debilitating, hospitalisation; no relief with meds
C5. Rigors, chills	Asymptomatic, transient, no meds, or non-narcotic meds relieve	Symptomatic, narcotic meds relieve	Prolonged symptoms, with limited response to narcotic meds	Debilitating, hospitalisation; no relief with meds
C6. Sweating (diaphoresis)	Episodic, transient	Frequent, short term	Frequent, drenching, disabling	Dehydration, requiring IV fluids/hospitalization > 24 hrs
C7. Weight gain	5% – 9.9%	10% – 19.9%	20% – 30%	NA
C8. Weight loss	5% – 9.9%	10% – 19.9%	20% – 30%	NA
D. Dermatologic				
D1. Alopecia	Subjective, transient	Objective, fully reversible	Patchy, wig used, partly reversible	Complete, or irreversible even if patchy

D2. Bullous eruption	Localised, asymptomatic	Localised, symptomatic, requiring treatment	Generalised, responsive to treatment; reversible	Prolonged, generalised, or requiring hospitalisation for treatment
D3. Dry skin	Asymptomatic, controlled with emollients	Symptoms eventually (1 – 2 wks) controlled with emollients	Generalised, interfering with ADL > 2 wks, persistent pruritis; partially responsive to treatment	Disabling for extended period, unresponsive to ancillary therapy and requiring study drug discontinuation for relief
D4. Injection site reaction	Local erythema, pain, pruritis, < few days	Erythema, pain, oedema, may include superficial phlebitis, 1 – 2 wks	Prolonged induration, superficial ulceration; includes thrombosis	Major ulceration necrosis requiring surgery
D5. Petechiae (without vasculitis)	Few, transient asymptomatic	Dependent areas, persistent up to 2 wks	Generalised, responsive to treatment; reversible	Prolonged, irreversible, disabling
D6. Photosensitivity	Transient erythema	Painful erythema and oedema requiring topical treatment	Blistering or desquamation, requires systematic corticosteroids	Generalised exfoliation or hospitalisation
D7. Pruritis	Localised, asymptomatic, transient, local treatment	Intense, or generalised, relieved by systematic medication	Intense or generalised; poorly controlled despite treatment	Disabling, irreversible
D8. Rash (not bullous)	Erythema, scattered macular/popular eruption; pruritis transient; TOC or no meds	Diffuse macular/popular eruption or erythema with pruritis; dry desquamation; treatment required	Generalised, moist desquamation, requires systemic corticosteroids; responsive to treatment; reversible	Exfoliative or ulcerating, or requires hospitalisation, or parenteral corticosteroids
D9. Induration/fibrosis/Thickening (not sclerodermal)	Localized, high density on palpation, reversible, no effect on ADL and not disfiguring	Local areas < 50% body surface, not disfiguring, transient interference with ADL, reversible	Generalized, disfiguring, interferes with ADL, reversible	Disabling, irreversible, systemic symptoms
E. Ear/Nose/Throat				
E1. Hearing loss	Transient, intermittent, no interference with function	Symptomatic, treatment required, reversible	Interferes with function; incomplete response to treatment	Irreversible deafness
E2. Sense of smell	Slightly altered	Markedly altered	Complete loss, reversible	Complete loss, without recovery
E3. Stomatitis	Asymptomatic	Painful, multiple, can eat	Interferes with nutrition, slowly reversible	Requires enteral support; residual dysfunction

E4. Taste disturbance (dysgeusia)	Transiently altered; metallic	Persistently altered; limited effect on eating	Disabling, effect on nutrition	NA
E5. Tinnitus	Intermittent, transient, no interference with function	Requires treatment, reversible	Disabling, or associated with hearing loss	Irreversible deafness
E6. Voice changes (includes hoarseness, loss of voice, laryngitis)	Intermittent hoarseness, able to vocalise	Persistent hoarseness, able to vocalise	Whispered speech, slow return of ability to vocalise	Unable to vocalize for extended duration
E7. Xerostomia (dry mouth)	Transient dryness	Relief with meds	Interferes with nutrition, slowly reversible	Extended duration interference with nutrition, requires parenteral nutrition
F. Eye/Ophthalmologic				
F1. Cataract	Asymptomatic, no change in vision, non-progressive	Symptomatic, partial visual loss, progressive	Symptoms impairing function, vision loss requiring treatment, including surgery	NA
F2. Conjunctivitis	Asymptomatic, transient, rapid response to treatment	Symptomatic, responds to treatment, changes not interfering with function	Symptoms prolonged, partial response to treatment, interferes with function	NA
F3. Lacrimation increased (tearing, watery eyes)	Symptoms not requiring treatment, transient	Symptomatic, treatment required, reversible	Unresponsive to treatment with major effect on function	NA
F4. Retinopathy	Asymptomatic, non-progressive, no treatment	Reversible change in vision; readily responsive to treatment	Disabling change in vision ophthalmological findings reversible, sight improves over time	Loss of sight
F5. Vision changes (e.g., blurred, photophobia, night blindness, vitreous floaters)	Asymptomatic, transient, no treatment required	Symptomatic, vision changes not interfering with function, reversible	Symptomatic, vision changes interfering with function	Loss of sight

F6. Xerophthalmia (dry eyes)	Mild scratchiness	Symptomatic without interfering with function, requires artificial tears	Interferes with vision/function, corneal ulceration	Loss of sight
G. Gastrointestinal				
G1. Anorexia	Adequate food intake, minimal weight loss	Symptoms requiring oral nutritional supplementation	Prolonged, requiring iv support	Requires hospitalization for nutritional support
G2. Constipation	Asymptomatic, transient, responds to stool softener, OTC laxatives	Symptomatic, requiring prescription laxatives, reversible	Obstipation requiring medical intervention	Bowel obstruction. Surgery required
G3. Diarrhea	Transient, increase of 2 – 3 stools/day over pre-treatment (no blood or mucus), OTC agents relieve	Symptomatic, increase 4 – 6 stools/day, nocturnal stools, cramping, requires treatment with prescription meds	Increase > 6 stools/day, associated with disabling symptoms, e.g., incontinence, severe cramping, partial response to treatment	Prolonged, dehydration, unresponsive to treatment, requires hospitalization
G4. Dyspepsia (heartburn)	Transient, intermittent, responds to OTC antacids, H-2 blockers	Prolonged, recurrent, requires prescription meds, relieved by meds	Persistent despite treatment, interferes with function, associated with GI bleeding	NA
G5. GI bleed (gastritis, gastric or duodenal ulcer diagnosed-define aetiology)	Asymptomatic, endoscopic finding, haemocult + stools, no transfusion, responds rapidly to treatment	Symptomatic, transfusion ≤ 2 units needed; responds to treatment	Haematemesis, transfusion 3 – 4 units, prolonged interference with function	Recurrent, transfusion > 4 units, perforation, requiring surgery, hospitalisation
G6. Haematochezia (rectal bleeding)	Haemorrhoidal, asymptomatic, no transfusion	Symptomatic, transfusion ≤ 2 units, reversible	Recurrent, transfusion > 3 – 4 units	> 4 units, hypotension, requiring hospitalization
G7. Hepatitis	Laboratory abnormalities, asymptomatic, reversible	Symptomatic laboratory abnormalities, not interfering with function, slowly reversible	Laboratory abnormalities persistent > 2 wks, symptoms interfere with function	Progressive, hepato-renal, anasarca, pre-coma or coma
G8. Nausea, or nausea/vomiting (use diagnostic term)	Transient, intermittent, minimal interference with intake, rapid response to meds	Persistent, recurrent, requires prescription meds, intake maintained	Prolonged, interferes with daily function and nutritional intake, periodic iv fluids	Hypotensive, hospitalization, parenteral nutrition, unresponsive to out-patient management

G9. Pancreatitis	Anylase elevation, intermittent nausea/vomiting, transient, responds rapidly to treatment	Amylase elevation with abdominal pain, nausea, occasional vomiting, responsive to treatment	Severe, persistent abdominal pain with pancreatic enzyme elevation, incomplete or slow response to treatment	Complicated by shock, haemorrhage (acute circulatory failure)
G10. Proctitis	Perianal pruritus, haemorrhoids (new onset), transient, or intermittent, relieved by OTC meds	Tenesmus or ulcerations, anal fissure, responsive to treatment, minimal interference with function	Unresponsive to treatment, marked interference with function	Mucosal necrosis with haemorrhage, infection, surgery required
H. Musculoskeletal				
H1. Avascular necrosis	Asymptomatic MRI changes, non-progressive	MRI changes and symptoms responsive to rest and analgesia	MRI changes, symptoms requiring surgical intervention	Wheelchair bound; surgical repair not possible
H2. Arthralgia	Intermittent transient symptoms, no meds or relieved by OTC meds	Persistent or recurrent symptoms, resolve with meds, little effect on function	Severe symptoms despite meds impairs function	Debilitating, hospitalisation required for treatment
H3. Leg cramps	Transient, intermittent, does not interfere with function	Recurrent symptoms, minimally interferes with function or sleep, responds to meds	Persistent, prolonged interference with function or sleep, partial or no response to meds	NA
H4. Myalgia	Occasional; does not interfere with function	Frequent, requires meds (non-narcotic); minor effects on function	Major change in function/lifestyle, narcotic pain meds	Debilitating, profound weakness, requires wheelchair, unresponsive to meds
I. Neuropsychiatric				
I1. Anxiety or Depression (mood alteration)	Symptomatic, does not interfere with function; no meds	Frequent symptoms, responds to meds; interferes with ADL at times	Persistent, prolonged symptoms, partial or no response to meds, limits daily function	Suicidal ideation or danger to self
I2. Cerebrovascular ischaemia	NA	Single transient ischaemic event, responsive to treatment	Recurrent transient ischaemic events	Cerebrovascular accident with permanent disability
I3. Cognitive disturbance	Subjective symptoms, transient, intermittent, not interfering with function	Objective symptoms, persisting, interferes with daily function occasionally	Persistent, or worsening objective symptoms; interferes with routine daily routine	Debilitating/disabling and permanent; toxic psychosis

14. Depressed consciousness (somnolence)	Observed, transient, intermittent, not interfering with function	Somnolence or sedation, interfering with function	Persistent, progressive, obtundation, stupor	Coma
15. Inability to concentrate	Subjective symptoms, does not interfere with function	Objective findings, interferes with function	Persistent, prolonged objective findings or organic cause	NA
16. Insomnia (in absence of pain)	Occasional difficulty sleeping, transient intermittent, not interfering with function	Recurrent difficulty sleeping; requires meds for relief; occasional interference with function	Persistent or worsening difficulty sleeping; severely interferes with routine daily function	NA
17. Libido decreased	Decrease in interest	Loss of interest; influences relationship	Persistent, prolonged interfering with relationship	NA
18. Peripheral motor neuropathy	Subjective or transient loss of deep tendon reflexes; function maintained	Objective weakness, persistent, no significant impairment of daily function	Objective weakness with substantial impairment of function	Paralysis
19. Peripheral sensory neuropathy (sensory disturbance)	Subjective symptoms without objective findings, transient, not interfering with function	Objective sensory loss, persistent, not interfering with function	Prolonged sensory loss or paresthesia interfering with function	NA
110. Seizure	NA	Recurrence of old seizures, controlled with adjustment of medication	Recurrence/exacerbation with partial response to medication	Recurrence not controlled, requiring hospitalization; new seizures
111. Vertigo (dizziness)	Subjective symptoms, transient, intermittent, no treatment	Objective findings, recurrent, meds relieve, occasionally interfering with function	Persistent, prolonged, interfering with daily function; partial response to medication	Debilitating without response to medication, hospitalization
J. Pulmonary				
J1. Asthma	Occasional wheeze, no interference with activities	Wheezing, requires oral meds, occasional interference with function	Debilitating, requires nasal O ₂	Requires ventilator assistance
J2. Cough	Transient, intermittent, occasional OTC meds relieve	Persistent, requires narcotic or other prescription meds for relief	Recurrent, persistent coughing spasms without consistent relief by meds, interferes with function	Interferes with oxygenation; debilitating

J3. Dyspnea	Subjective, transient, no interference with function	Symptomatic, intermittent or recurring, interferes with exertional activities	Symptomatic during daily routine activities, interferes with function, treatment with intermittent nasal O ₂ relieves	Symptomatic at rest, debilitating, requires constant nasal O ₂
J4. Pleuritic pain (pleurisy)	Transient, intermittent symptoms, no treatment or OTC meds relieve	Persistent symptoms, requires prescription meds for relief	Prolonged symptoms, interferes with function, requires frequent narcotic pain relief	Debilitation, requiring hospitalisation
J5. Pneumonitis (pulmonary infiltrates)	Asymptomatic radiographic changes, transient, no treatment required	Symptomatic, persistent, requiring corticosteroids	Symptomatic, requiring treatment including O ₂	Debilitating, not reversible; or requiring assisted ventilation
J6. Pulmonary function decreased (FVC or carbon monoxide diffusion capacity – DLCO)	70% – 90% of pre-treatment value	51% – 75% of pre-treatment value	26% – 50% of pre-treatment value	≤ 25% of pre-treatment value
Laboratory Data				
K. Haematology				
K1. Hgb (g/dl) decrease from pre-treatment	1.0 – 1.4	1.5 – 2.0	2.1 – 2.9, or Hgb < 8.0, > 7.0	≥ 3.0; or Hgb < 7.0
K2. Leukopenia (total WBC) × 1000	3.0 – 3.9	2.0 – 2.9	1.0 – 1.9	< 1.0
K3. Neutropenia (× 1000)	1.5 – 1.9	1.0 – 1.4	0.5 – 0.9	< 0.5
K4. Lymphopenia (× 1000)	1.5 – 1.9	1.0 – 1.4	0.5 – 0.9	< 0.5
K5. Platelets (× 1000)	75 – LLN	50 – 74.9	20 – 49.9; platelet transfusion required	< 20; recurrent platelet transfusions

L. Chemistry				
L1. Hypercalcaemia (mg/dl)	1.1 × ULN – 11.5	11.6 – 12.5	12.6 – 13.5; or symptoms present	> 13.5; or associated coma
L2. Hyperglycemia (mg/dl) Fasting	140 – 160	161 – 250	251 – 500	> 500, or associated with ketoacidosis is
L3. Hyperkalaemia (mmol/l)***	5.5 – 5.9	6.0 – 6.4	6.5 – 7.0 or any ECG change	> 7.0 or any arrhythmia
L5. Hypocalcaemia (mg/dl)	0.9 × LLN – 7.8	7.7 – 7.0	6.9 – 6.5; or associated with symptoms	< 6.5 or occurrence of tetany
L6. Hypoglycemia (mg/dl)	55 – 64 (no symptoms)	40 – 54 (or symptoms present)	30 – 39 (symptoms impair function)	< 30 or coma
L7. Hyponatraemia (mmol/l)***	-	125 – 129	120 – 124	< 120
L8. Hypokalaemia (mg/dl)***	-	3.0 – 3.4	2.5 – 2.9	< 2.5
L9. CPK (also if polymyositis- disease)***	> ULN – 1.5 × ULN	> 2.5 – 5.0 × ULN	> 5.0 – 10.0 × ULN	> 10.0 × ULN
L10. Serum uric acid	1.2 – 1.6 × ULN	1.7 – 2.9 × ULN	3.0 – 5.0 × ULN or gout	NA
L11. Creatinine (mg/dl)***	> 1 – 1.5 × Baseline; > ULN – 1.5 × ULN	> 1.5 – 3.0 × Baseline; > 1.5 – 3.0 × ULN	> 3.0 baseline; > 3.0 – 6.0 × ULN	> 6.0 × ULN
L12. SGOT (AST)	1.2 – 1.5 × ULN	1.6 – 3.0 × ULN	3.1 – 8.0 × ULN	> 8.0 × ULN
L13. SGPT (ALT)	1.2 – 1.5 × ULN	1.6 – 3.0 × ULN	3.0 – 8.0 × ULN	> 8.0 × ULN
L14. Alkaline phosphatase	1.1 – 1.5** × ULN	1.6 – 3.0 × ULN	3.0 – 5.0 × ULN	> 5.0 × ULN
L15. T. bilirubin	1.1 – 1.4 × ULN	1.5 – 1.9 × ULN	2.0 – 3.0 × ULN	> 3.0 × ULN
L16. LDH	1.3 – 2.4 × ULN	2.5 – 5.0 × ULN	5.1 – 10 × ULN	> 10 × ULN

M. Urinalysis					
M1. Haematuria	Micro only	Gross, no clots	Clots, transfusion < 2 units	Transfusion required	
M2. Proteinuria (per 24 h)	300 – 500 mg (tr/1+)	501 – 1999 mg (2+)	2 – 5.0 g (3+) nephrotic syndrome	5.0 g (4+) anasarca	
M3. WBC in urine	NA	NA	Indicating acute interstitial nephritis	Associated with acute renal failure	
M4. Uric acid crystals	Present without symptoms	NA	With stones or symptoms of stones (e.g., renal colic)	Causing renal outflow obstruction and hospitalization	

*: in L11, 1.5 – 1.8 \times ULN is changed to 1.4 – 1.8 \times ULN.

**: in L14, 1.1 – 2.0 \times ULN is changed to 1.1 – 1.5 \times ULN.

***: in L3, L7 and L8, mg/dl is changed to mmol/l.

****: NCI CTC grade.

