**M. Urinalysis**

M1. Haematuria	Micro only	Gross, no clots	Clots, transfusion < 2 units	Transfusion required
M2. Proteinuria (per 24 h)	300 – 500 mg (tr/1+)	501 – 1999 mg (2+)	2 – 5.0 g (3+) nephrotic syndrome	5.0 g (4+) anasarca
M3. WBC in urine	NA	NA	Indicating acute interstitial nephritis	Associated with acute renal failure
M4. Uric acid crystals	Present without symptoms	NA	With stones or symptoms of stones (e.g., renal colic)	Causing renal outflow obstruction and hospitalization

OTC = over-the-counter medication; ADL = activities of daily living; IV = intravenous; ECG = electrocardiogram; CHF = congestive heart failure; MRI = magnetic resonance imaging; Hb = haemoglobin; LLN = lower limit of normal; ULN = upper limit of normal; WBC = white blood cells; SLE = systemic lupus erythematosus; ANA = antinuclear antibodies; H-2 blockers = histamine-2 blockers; FVC = forced vital capacity

\* For CPK and Creatinine NCI CTC grading will be used. For CPK the following gradings apply: Grade 1: > ULN – 2.5 × ULN, Grade 2: > 2.5 – 5.0 × ULN; Grade 3: > 5.0 – 10.0 × ULN; Grade 4: > 10.0 × ULN; For Creatinine the following gradings apply: Grade 1: > 1 – 1.5 × Baseline; > ULN – 1.5 × ULN; Grade 2: > 1.5 – 3.0 × Baseline; > 1.5 – 3.0 × ULN; Grade 3: > 3.0 × Baseline; > 3.0 – 6.0 × ULN; Grade 4: > 6.0 × ULN.

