10.3.2.2 Assessment of Shift from Baseline in Clinical Laboratory Variables

The baseline and post-baseline laboratory observations will be categorized as Grade 1, Grade 2, Grade 3, and Grade 4 according to OMERACT criteria (Rheumatology Common Toxicity Criteria v.2.0). For creatine phosphokinase and creatinine NCI CTC criteria will be used.

For each laboratory variable, shift tables will be generated that cross tabulate the subjects as deemed appropriate by "as treated" treatment group:

- Category of the baseline value versus category of the final value.
- Category of the baseline value versus maximum category.
- Category of the baseline value versus minimum category.

Note that the minimum/maximum category is used, rather than the category of the minimum/maximum value. The two may be different due to variation in the reference range.

No statistical tests will be performed for this analysis.

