10.3.2.3 Assessment of Potentially Clinically Significant Laboratory Variables

The criteria for potentially clinically significant laboratory values will be determined by OMERACT criteria of Grade 3 or 4. For creatine phosphokinase and creatinine, NCI CTC criteria will be used.

The number and percentage of subjects meeting the criteria for potentially clinically significant laboratory values will be summarized by "as treated" treatment group. Only subjects with worsening in grade compared to baseline grade will be captured.

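### SAP Appendix A ends CPK Grade 1 at 1.5 × ULN but starts Grade 2 above 2.5 × ULN, so CPK values between those limits have no grade in the Period 1 shift tables

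*SAP*

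**What the plan says.** SAP 10.3.2.2 defines the laboratory shift tables for Period 1. On the categories it says: "The baseline and post-baseline laboratory observations will be categorized as Grade 1, Grade 2, Grade 3, and Grade 4". The default grading is OMERACT, with one exception: "For creatine phosphokinase and creatinine NCI CTC criteria will be used". The tables cross baseline category with final, maximum and minimum category, by treatment group as treated.

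The grades are printed in SAP Appendix A. Its header note says of CPK and creatinine that "the criteria in this table is replaced by the NCI CTC grade, as the NCI CTC grade is used for analysis for these two parameters", so row L9, labelled "CPK (also if polymyositis- disease", is presented as the NCI CTC scale. In that row Grade 1 stops at 1.5 × ULN and Grade 2 begins above 2.5 × ULN.

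The protocol prints the same scale in the footnote to Appendix N, introduced by "For CPK the following gradings apply", and there the two grades meet: "Grade 1: > ULN – 2.5 × ULN, Grade 2: > 2.5 – 5.0 × ULN".

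Potentially clinically significant values rest on the upper grades only (SAP 10.3.2.3): "The criteria for potentially clinically significant laboratory values will be determined by OMERACT criteria of Grade 3 or 4", again with NCI CTC for CPK and creatinine.

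**The concern.** A grading scale used to build a shift table has to place every value in exactly one category. Row L9 does not. A CPK of 1.4 × ULN is Grade 1, a CPK of 2.0 × ULN is nothing, and a CPK of 2.6 × ULN is Grade 2. The SAP leaves it to the programmer whether a value in the gap becomes missing or falls in with the ungraded normal values. Either choice understates mild CPK elevation in the tables, and the two choices give different tables.

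The SAP also disagrees with the protocol on a cut-point for the same analysis. The two documents could lead two competent programmers to different Grade 1 counts.

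**Working it through.** The documents state no derived figure to reproduce here. The check sets the two printed scales side by side, grades test values on each, and measures the gap.

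**1. The two scales (multiples of ULN)**

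| Grade | SAP Appendix A, row L9 | Protocol Appendix N, footnote |
|---|---|---|
| 1 | > 1.0 to 1.5 | > 1.0 to 2.5 |
| 2 | > 2.5 to 5.0 | > 2.5 to 5.0 |
| 3 | > 5.0 to 10.0 | > 5.0 to 10.0 |
| 4 | > 10.0 | > 10.0 |

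Only the Grade 1 upper limit differs. The creatinine limits agree between the two documents.

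**2. Test values on each scale**

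| CPK (× ULN) | SAP row L9 | Protocol |
|---|---|---|
| 1.2 | 1 | 1 |
| 1.5 | 1 | 1 |
| 1.51 | none | 1 |
| 2.0 | none | 1 |
| 2.5 | none | 1 |
| 2.51 | 2 | 2 |
| 5.0 | 2 | 2 |
| 5.01 | 3 | 3 |
| 10.0 | 3 | 3 |
| 10.1 | 4 | 4 |

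Moving the SAP limit to 2.5 × ULN turns the three ungraded values into Grade 1 and changes no other grade in the list.

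**3. Is it an intended change?** The notes below SAP Appendix A list its edits to the source table: L11, L14, and the units of L3, L7 and L8. None mentions a new Grade 1 limit for CPK. An intended change would also have had to move the Grade 2 lower limit to 1.5 to keep the scale continuous.

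**4. Size by width.** Gap ÷ protocol Grade 1 interval = (2.5 − 1.5) ÷ (2.5 − 1.0) = 1.0 ÷ 1.5 = 0.67.

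**5. Size by share of values.** The documents give no CPK distribution, so this step is an assumption that shows a range only. For a lognormal CPK with median m (× ULN) and log-SD s, write F(x) = Φ((ln x − ln m) ÷ s). The share of protocol Grade 1 values that fall in the gap is [F(2.5) − F(1.5)] ÷ [F(2.5) − F(1.0)].

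Example with m = 1.0 and s = 0.4: (0.989 − 0.845) ÷ (0.989 − 0.500) = 0.144 ÷ 0.489 ≈ 0.30.

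| Assumed median (× ULN) | Share in gap, s = 0.4 to 1.0 |
|---|---|
| 0.3 | 2% to 38% |
| 0.6 | 11% to 45% |
| 0.8 | 20% to 48% |
| 1.0 | 30% to 51% |
| 1.2 | 40% to 53% |
| 1.5 | 54% to 55% |

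The share exceeds one half throughout the log-SD range only at the highest median tried, 1.5 × ULN. At medians below ULN it is a minority in every case tried.

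**6. Which outputs use the Grade 1 limit**

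- Shift tables, SAP 10.3.2.2: yes. They are specified for Period 1, and the SAP plans no statistical test on them. The long-term laboratory section (SAP 10.3.3) contains no shift tables.
- Potentially clinically significant values, SAP 10.3.2.3 and 10.3.3.2: these start at Grade 3, where the limits match the protocol.
- CPK as an adverse event of special interest, SAP Table 11: found by a single preferred term, with no laboratory grade involved.
- Mean change from baseline, SAP 10.3.2.1: uses the continuous CPK value, so results in the gap enter in full.

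**The case against.** The strongest reply is that the intended rule is clear. SAP 10.3.2.2, 10.3.2.3 and 10.3.3.2 all name NCI CTC for CPK, Protocol 8.1.5.3 does the same, and the Appendix N footnote prints a complete scale. A programmer working from the protocol would meet no gap. This limits the likely harm but does not remove the conflict: the SAP presents its own row as the scale used for analysis, and someone following the SAP alone would reproduce the gap.

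A second reply is that the 1.5 may be a misread digit in the text version of the PDF. Other small differences exist between the two copies of the table; for example, the lower bound for Grade 1 pulmonary function (J6) is 70% in the SAP and 76% in the protocol. The possibility stands, and the cell should be checked against the PDF. Nothing in the row itself points to a misreading. The creatinine row just below does use 1.5 × ULN as its Grade 1 limit, so a copying slip is plausible, but that too is conjecture.

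A third reply is that the consequence is small, and this stands in full. A reader might infer from the two-thirds figure that the tables lose most Grade 1 elevations. Width is not a share of values, and step 5 shows a minority under most of the assumed distributions. A reader might also infer that the special-interest counts for CPK are wrong, or that mild elevations vanish from the drug–placebo comparison. The documents do not support either: the special-interest search uses a preferred term, and the mean-change analysis compares the arms on all CPK values.

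**Conclusion.** The point holds in a narrow form. SAP Appendix A row L9 leaves CPK values above 1.5 and up to 2.5 × ULN without a grade and contradicts the protocol on that one limit. If the row is programmed as printed, some Grade 1 elevations have no category in the descriptive Period 1 CPK shift tables. How many cannot be derived from the documents, and no subject count should be attached to it.

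The Grade 3 and 4 limits, the preferred-term special-interest counts, the mean-change analyses and all efficacy results are untouched. One programming detail needs care. The potentially clinically significant tables count only subjects whose grade worsens from baseline, and a baseline value in the gap has no grade to compare with. Such a value is below Grade 3 on either scale, so a later Grade 3 or 4 value is a worsening, but the program should not drop that subject because the baseline grade is missing.

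The conclusion assumes that the printed 1.5 is what the SAP contains and that the row, as its header note says, governs the analysis. It is worth correcting because it is a wrong threshold in an analysis table and the sponsor's own protocol already supplies the consistent value.

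**What to change.** In SAP Appendix A, row L9, change the Grade 1 upper limit from 1.5 × ULN to 2.5 × ULN, so that it agrees with the footnote to Protocol Appendix N and meets the start of Grade 2. Check that the grading format in the laboratory programs uses 2.5, and that a value of 2.0 × ULN returns Grade 1.

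The cost is one table cell and one format check. If the Period 1 CPK shift tables have already been produced from the SAP row, they need a rerun. No other row, output or protocol text has to change.
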